	APPENDICES	30
	APPENDIX A: SCHEDULE OF EVENTS	31

LIST OF ABBREVIATIONS

The following abbreviations describe terms, documents and study personnel used in the conduct of this study protocol.

AE	Adverse Event/Adverse Experience
CC	Coordinating Centre
CIOMS	Council for international Organizations of Medical Sciences
CRF	Case Report Form
CCTS	Centre for Clinical Trial Support
EC	Ethics Committee
ICH	International Conference on Harmonisation
IP	Investigational Product
pCRF	Paper Case Report Form
GCP	Good Clinical Practice
ICF	Informed Consent Form
PHI	Personal Health Information
PI	Principal Investigator
PM	Product Monograph
QI	Qualified Investigator
REB	Research Ethics Board
RCT	Randomized Controlled Trial
SAE	Serious Adverse Event/Serious Adverse Experience
SOP	Standard Operating Procedure
SRI	Sunnybrook Research Institute
SUADR	Serious and Unexpected Adverse Drug Reaction
TMF	Trial Master File

PROTOCOL SUMMARY

Protocol Title (Short Title)	DIAgnosing GDM usiNg Oral Sugar InStead (DIAGNOSIS)
	Randomized crossover study comparing the standard glucose beverage and Dex4® tablets for 2 hour oral glucose tolerance testing in pregnant women with a positive screen on the 50g glucose tolerance challenge for gestational diabetes
Protocol Number	Assigned REB number 418-2018.
Phase	II
Study Design	Phase II randomized controlled crossover study
Study Duration	6 months
Setting	Single-centre
Sample Size	28 required by power calculation, aiming to recruit 42 (accounting for 33% loss)
Main Inclusion Criteria	
 • Positive 50g GCT result between 7.8-11.0 mmol/L • singleton pregnancy
Primary Outcome(s):	2 hour serum glucose value after the carbohydrate challenge. The study is powered to assess equivalence between Dex4® tablets and 75g of glucose beverage.
Secondary Outcome(s):	Side effects associated with Dex4® tablets and participant preference of using Dex4® tablets or the standard glucose beverage for OGTT testing.
Investigational Product (IP) and Planned Use	The investigational product to be used is (Dex4®) dextrose monohydrate tablets, containing 4g of dextrose monohydrate per tablet equivalent to 3.64g of dextrose anhydrous. After a minimum 8 hour fast, 21 Dex4® tablets will be ingested over the span of 5 minutes. Venous blood sampling for serum glucose will be taken prior to ingestion , and 1 and 2 hours (+/- 15 minutes) after ingesting the Dex4® tablets.

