4 STUDY DESIGN

4.1 General Design

Our project is a population-based, prospective randomized crossover study. Women who fall into the screen positive group of the 50g GCT (1 hour serum glucose of 7.8-11 mmol/L) will be offered participation in the study. 28 Participants will be recruited and will be randomly assigned using a pre-populated allocation table to take either the standard OGTT test (75g of glucose beverage) first or the alternative OGTT test (21 Dex4® tablets) first. The first test will be referred to as OGTT-1 and the second test will be referred to as OGTT-2. After completing OGTT-1 at the first test appointment, a questionnaire about pregnancy, health, diet and exercise habits, and side effects from the first test will be completed by the participant (Questionnaire A). After completing OGTT-2 at their second test appointment, a questionnaire about side effects from the second test and test preference will be completed by the participant (Questionnaire B). Each woman will complete both tests within one week and each subject will serve as their own control. Results will be kept blinded in the case report forms until both OGTT tests are done. Serum glucose will be measured using the same internationally standardised glucose-oxidase method (RocheDiagnosis) in the Sunnybrook Biochemistry lab. After serum glucose measurement, all results will be sent to the research team but only the standard of care glucose beverage test data will appear in electronic (or classical) medical records and be used for GDM diagnosis.

The following data will be collected by questionnaire at the first OGTT appointment:

- Estimated date of delivery
- # of previous pregnancies
- Previous diagnosis of GDM
- Pre-pregnancy weight (kg);
- Height (cm);
- Ethnic group (Caucasian, Indigenous, Hispanic, South Asian, East Asian, African, Middle Eastern, Other)
- History of macrosomic infant - ≥ 4000 g
- Polycystic ovary syndrome (yes-no);
- Medication (for corticosteroid use);
- First degree family history of T2DM
- Length of fast (hrs)
- Side effects (nausea, vomiting, headache, dizziness, sweating, other)

The following data will be collected by questionnaire at the second OGTT appointment:

- Side effects
- Preference for Dex4® or glucose beverage

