4.2 Primary Outcomes/Endpoint(s)

The primary outcome measures are fasting 1hr and 2hr PG levels from the Dex4® and glucose beverage OGTTs. Serum glucose values after a carbohydrate load have significant intra-individual variation, if done on the same person but at a different time the results can vary up to 16.7% (21) The two tests will be considered equivalent if the difference between them is less than or equal to 20%.

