6.2.1 Administration of Intervention

Participants will be asked to ingest 21 Dex4® tablets and no more than 300ml of water within 5 minutes. Blood draws will be performed at fasting (before ingesting the dextrose monohydrate tablets), as well as 1 hour after (+/- 15 minutes) and 2 hours (+/- 15 minutes) after ingesting the dextrose monohydrate tablets.

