10.2 Sample Size Considerations

Serum glucose values after a carbohydrate load have significant intra-individual variation, if done on the same person but at a different time the results can vary up to 16.7% (21) The two tests will be considered equivalent if the difference between them is less than or equal to 20%. For a mean one hour (+/- 15 minutes) post 75g carbohydrate load serum blood glucose of 10.6 mmol/L (standard deviation of 1.78 mmol/L) a sample of 28 will provide 80% power at alpha of 0.05 for a test of equivalence with Dex4® tablets assuming a 20% margin of equivalence. The sample size calculation was carried out using PASS Version 12 (Hintze, J. (2014). NCSS, LLC. Kaysville, Utah.) Accounting for loss to follow up of 33%, 42 women will need to be recruited, respectively. Based on data from Alberta, 20% of women screen positive on an 50g GCT (22). Approximately 230 women deliver at Sunnybrook every month, of those 45 will screen positive on the GCT. Assuming a 20% successful recruitment rate we should be able to complete recruitment in 4-6 months.

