10.4 Final Analysis Plan

Serum glucose values after a carbohydrate load have significant intra-individual variation, if done on the same person but at a different time the results can vary up to 16.7% (21) The two tests will be considered equivalent if the difference between them is less than or equal to 20%. For a mean one hour post 75g carbohydrate load serum blood glucose of 10.6 mmol/L (standard deviation of 1.78 mmol/L) a sample of 28 will provide 80% power at alpha of 0.05 for a test of equivalence with Dex4® tablets assuming a 20% margin of equivalence. The sample size calculation was carried out using PASS Version 12 (Hintze, J. (2014). NCSS, LLC. Kaysville, Utah.) Accounting for loss to follow up of 33%, 42 women will need to be recruited, respectively.

To evaluate equivalence, the mean of the differences at each time point (fasting, 1 hr and 2 hrs after glucose beverage/Dex4® tablets) will be calculated and a two-sample equivalence-test will be used to compare the means. Based on previous reports of intra-individual variation in 2 hour OGTT of 16.7% for blood glucose measurement (21), Dex4® tablets will be considered equivalent to glucose beverage if the equivalence margin is less than or equal to 20%.

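### Fasting glucose, drawn before either load, is tested as a primary equivalence outcome instead of serving as the visit baseline for the 1 h and 2 h comparisons

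*Protocol*

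**What the plan says.** Three places in the protocol fix the role of the fasting sample.

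- Section 4.2: "The primary outcome measures are fasting 1hr and 2hr PG levels from the Dex4® and glucose beverage OGTTs".
- Section 10.4: "the mean of the differences at each time point (fasting, 1 hr and 2 hrs after glucose beverage/Dex4® tablets) will be calculated", after which "a two-sample equivalence-test will be used to compare the means". One method and one 20% margin serve all three time points, and no baseline term is mentioned.
- Section 6.2.1: "Blood draws will be performed at fasting (before ingesting the dextrose monohydrate tablets", with the 1 h and 2 h draws afterwards. Section 6.1.4.3 gives the same order.

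The design is a crossover: "Each woman will complete both tests within one week and each subject will serve as their own control" (section 4.1). The Protocol Summary names a narrower primary outcome, "2 hour serum glucose value after the carbohydrate challenge", so fasting glucose is primary in one place and not in another.

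**The concern.** A value taken before ingestion cannot be changed by what is then ingested. With randomised order and no carry-over from the first test, the expected fasting difference between product visits is zero whatever the tablets do. A positive equivalence result at fasting is therefore close to guaranteed by design, yet under section 4.2 it would count as primary evidence about the product.

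The same sample does carry useful information. The protocol treats day-to-day variation within a woman (up to 16.7%) as its main difficulty and bases the 20% margin on it. Fasting glucose is a measure, at both visits, of the woman's state just before the load. Length of fast is listed only for the first appointment (sections 4.1 and 11.2), so among the listed items fasting glucose is the only such measure at the second visit. Left unused, whatever part of the day-to-day shift already shows at fasting stays in the 1 h and 2 h differences as noise.

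**Working it through.** **Inputs.** From section 10.2: "serum blood glucose of 10.6 mmol/L (standard deviation of 1.78 mmol/L" at 1 h; margin 20%, so 0.20 × 10.6 = 2.12 mmol/L; "a sample of 28 will provide 80% power at alpha of 0.05 for a test of equivalence with Dex4® tablets". Not in the protocol: whether 1.78 is a between-woman or within-woman SD; the correlation r between a woman's fasting difference and her post-load difference; the fasting SD; any 2 h mean or SD. The figures below therefore apply to 1 h only, and r is shown as a range.

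**The plan's own figure.** Two one-sided t-tests at 5% each, true difference 0, SD 1.78, margin 2.12:
- unpaired two-group test: 13 per group, 26 in total, close to the stated 28 (14 per group gives 84.5% power);
- crossover with no within-woman correlation: 14 in total;
- recruitment: 28 / (1 − 0.33) = 41.8, so 42, as stated.

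The 28 is thus approximately an unpaired calculation. The adjustment below works on within-woman differences, so its reference is an unadjusted paired analysis, not the two-sample test as written.

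**Reference: paired, unadjusted, 28 completers, no within-woman correlation.** SD of differences = 1.78 × √2 = 2.52. Standard error = 2.52 / √28 = 0.476. With 26 degrees of freedom the 90% interval has half-width 1.706 × 0.476 = 0.81 mmol/L. Power is 99.3% at true difference 0, and 70.0% at an assumed true difference of 10% (1.06 mmol/L).

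**Adding the fasting difference as covariate.** The SD of differences is multiplied by √(1 − r²). Estimating the slope costs a factor of about √(1 + 1/(28 − 4)) = 1.021 in interval width.

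| r | √(1 − r²) | Narrowing before cost | Width after cost | Power at 1.06, before cost | Power at 1.06, after cost |
|---|---|---|---|---|---|
| 0 | 1.000 | 0% | 1.021 | 70.0% | 68% |
| 0.2 | 0.980 | 2% | 1.000 | 71.5% | 70% |
| 0.3 | 0.954 | 5% | 0.974 | 73.5% | 72% |
| 0.5 | 0.866 | 13% | 0.884 | 80.5% | 79% |

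The last column uses 25 degrees of freedom and the factor 1.021. At true difference 0, power stays at about 99% or above in every row.

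**Subtracting fasting instead.** Change from fasting multiplies the SD of differences by √(1 + k² − 2rk), where k is the fasting SD over the post-load SD. It helps only if r > k/2. At k = 0.3 and r = 0 the factor is √1.09 = 1.044, the SD rises to 2.63 and power at 1.06 falls to 66.8%.

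**The case against.** **Covariates belong in the SAP.** That is fair for the covariate alone: silence in section 10.4 on adjustment would be no finding, and nothing there forbids it. But the protocol is not silent about the fasting value. It makes it a primary outcome and names its test, and an SAP that gave it only a baseline role would have to depart from sections 4.2 and 10.4.

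**Bias.** A reader might infer that unadjusted day-to-day shifts bias the comparison. The documents do not support this. Order is randomised, so such shifts are random error already carried by the standard error. The design also limits them: both tests within a week, the same assay, at least 8 hours of fasting, and no alcohol or non-routine exercise between tests. Removing chance fasting imbalance and narrowing the interval are largely one benefit, not two.

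**Need.** A reader might also infer that the trial fails without adjustment. It does not: in a paired analysis with zero true difference there is almost nothing to gain. A useful gain appears only with a true difference of some size and r above about 0.2, and both are assumptions.

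**Raw levels are the right target.** The OGTT is read on the 1 h and 2 h levels themselves. This stands, and it is why the fasting value should enter as a covariate and not be subtracted.

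**Conclusion.** The point holds in two parts of unequal certainty. It is clear from the protocol alone that a pre-load measurement is misplaced as a primary equivalence outcome; confidence is high. That the same measurement would sharpen the 1 h and 2 h comparisons is likely but of unknown size; confidence is moderate. Relative to an unadjusted paired analysis, the net narrowing is nil at r of about 0.2, about 3% at r = 0.3 and about 12% at r = 0.5. The power figures rest on 28 completers, a 10% true difference, an SD of differences of 2.52 and the 1 h mean; none can be carried to 2 h without a 2 h mean and SD. Severity is low to moderate. The unpaired test in a crossover and the conflicting primary time points are separate matters, although the fix assumes that pairing is settled.

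**What to change.** 1. In sections 4.2 and 10.4, remove fasting glucose from the primary equivalence outcomes. Report the fasting values and their within-woman difference descriptively, as a check that the two visits were comparable. The check is useful because section 6.1.3 lets the two tests be run by different staff or in different places.
2. For the 1 h and 2 h values, analyse the within-woman difference (tablets minus beverage), regressed on the within-woman fasting difference and period. Centre the fasting difference on zero, its expected value under randomised order, so that the product effect is read at equal fasting glucose. Centring on the sample mean would return, in balanced sequences, the unadjusted estimate.
3. Judge equivalence on the adjusted difference and report the unadjusted paired difference alongside. Fix this before any results are seen.

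Cost: a short text amendment and no new data. The model spends one degree of freedom on the fasting difference and one on period. If r turns out to be about 0.2 or less there is no net gain, and at r = 0 the interval is about 2% wider.

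### The deciding time point is contradictory, the named two-sample test does not match the paired design, and the sentences that declare equivalence do not use the test

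*Protocol*

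**What the plan says.** **Time point.** The Primary Outcome(s) row of the Protocol Summary gives "2 hour serum glucose value after the carbohydrate challenge". Section 4.2 says "The primary outcome measures are fasting 1hr and 2hr PG levels from the Dex4® and glucose beverage OGTTs". The sample size in section 10.2, repeated in section 10.4, rests on a third choice: "For a mean one hour (+/- 15 minutes) post 75g carbohydrate load serum blood glucose of 10.6 mmol/L", with a standard deviation of 1.78 mmol/L.

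**Test.** Section 4.1 describes a crossover in which "each subject will serve as their own control". To evaluate equivalence, section 10.4 and the Statistical Analysis row of the Protocol Summary take the mean of the differences at fasting, 1 h and 2 h, and then say "a two-sample equivalence-test will be used to compare the means". Section 10.2 claims "80% power at alpha of 0.05 for a test of equivalence" from 28 women with a 20% margin.

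**Decision.** Two sentences declare equivalence. The first, in section 10.4 and the Protocol Summary, is "Dex4® tablets will be considered equivalent to glucose beverage if the equivalence margin is less than or equal to 20" per cent. The second, in sections 4.2, 10.2 and 10.4, is "The two tests will be considered equivalent if the difference between them is less than or equal to 20" per cent. Section 10.4 contains both.

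**The concern.** Equivalence is the only primary objective (section 3.1), so the protocol should fix one time point or set of time points, one test and one pass rule. It fixes none of the three cleanly.

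- The primary outcome differs between places, and no place says whether one or all time points must pass. The fasting sample is drawn before the load is taken (sections 6.1.4.3 and 6.2.1), so it cannot show that the two loads are equivalent, yet section 4.2 lists it as primary.
- The data are paired by design, but the named test is two-sample.
- The margin is a constant set in advance, and the bare difference carries no allowance for sampling error. Neither sentence refers to the result of the test.

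The same data could therefore be called equivalent or not, depending on which sentence and which time point is followed after the results are known.

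**Working it through.** **Inputs from the protocol (section 10.2):** 1 h mean 10.6 mmol/L, SD 1.78 mmol/L, margin 20%, alpha 0.05, power 80%, 28 women, 33% loss. Margin in units: 0.20 × 10.6 = 2.12 mmol/L.

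**Assumed, not in the protocol:** within-woman correlation ρ from 0 to 0.8, equal SD under both loads, 0.05 per side. No 2 h mean or SD is given, so all figures below are for 1 h.

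**The plan's own figure.** TOST with true difference 0 and two independent groups needs 13 per group, 26 in total (power 80.8%). A total of 28 gives 84.5%. A paired test at ρ = 0 needs 14 women, and fewer as ρ rises. The nearest match to 28 is thus a total for two parallel groups. No paired or crossover variant tried at true difference 0 gives 28. The recruitment figure follows: 28 / (1 − 0.33) = 41.8, so 42.

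**What a paired TOST requires with 28 pairs.** SD of differences = 1.78 × √(2(1 − ρ)). Half-width of the 90% CI = 1.703 × SD of differences / √28. Largest passing observed difference = 2.12 − half-width.

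| ρ | SD of differences | Half-width | Largest passing difference |
|---|---|---|---|
| 0 | 2.52 | 0.81 | 1.31 mmol/L (12.4%) |
| 0.3 | 2.11 | 0.68 | 1.44 mmol/L (13.6%) |
| 0.5 | 1.78 | 0.57 | 1.55 mmol/L (14.6%) |
| 0.8 | 1.13 | 0.36 | 1.76 mmol/L (16.6%) |

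An observed 18% difference is 0.18 × 10.6 = 1.91 mmol/L. It is below 20%, and the margin is 20%, so both declaring sentences are met. At ρ = 0.8 the upper 90% limit is 1.91 + 0.36 = 2.27 mmol/L, above 2.12. At lower ρ it is higher still. The paired TOST therefore fails throughout the assumed range.

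**If the difference sentence decided alone.** With a true difference of 2.12 mmol/L, the observed mean difference is equally likely to fall on either side of 2.12, so the rule passes 50% of the time whatever the SD. A paired TOST passes 5%.

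**Two-sample against paired TOST on the same 28 pairs.** The two-sample version (54 degrees of freedom) is simulated; the paired version is computed exactly. Entries are the percentage declared equivalent at ρ = 0 / 0.5 / 0.8.

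| True difference | Two-sample | Paired |
|---|---|---|
| 0 | 99.4 / over 99.9 / 100 | 99.3 / 100 / 100 |
| 5% | 95 / 99 / over 99.9 | 95 / 99.8 / 100 |
| 10% | 71 / 78 / 87–88 | 70 / 92 / 99.9 |
| 15% | 29 / 23 / 13 | 29 / 46 / 78 |
| 20% | 5.0 / 1.1 / 0.03 | 5.0 / 5.0 / 5.0 |

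With positive correlation the two-sample form errs on the strict side. It costs little near 0 and most at intermediate differences.

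**The case against.** The strongest reply is that the intent can be recovered. Section 10.4 introduces the equivalence test as the means of evaluating equivalence, the next sentence gives 20%, and sections 5, 10.2 and 10.4 each power a test of equivalence at alpha 0.05 with a 20% margin. The natural reading is TOST against 20% with a loosely worded closing sentence. That largely stands, and it limits what can be claimed:

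- A reader might infer that the trial cannot fail, because the margin sentence is always true, or that its false-positive rate is 50%. Each follows only if one declaring sentence is taken literally and the test named in the same section is set aside. The protocol as a whole does not support that.
- A reader might infer that the two-sample test inflates error or leaves the trial underpowered. It does neither: error at the margin is at most about 5%, and power at a true difference of 0 is at least 99%.
- A reader might infer that an independent-groups analysis is certainly planned, or that the sample size was certainly derived for parallel groups. Two-sample can also mean comparing period differences between the two sequence groups, which is a valid crossover analysis. The protocol does not describe that, but its reference to the mean of the differences leaves the matter open.

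The reply does not reach the time-point conflict. An SAP, which is not shown here, could not settle that without contradicting at least one place in the protocol. Nor does probable intent amount to a stated rule, as the 18% example shows.

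**Conclusion.** The point holds as a set of contradictions and unclear wording to be settled before data are seen; it does not show an invalid trial.

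- **Firmest part:** the deciding time point is 2 h, or fasting, 1 h and 2 h, or 1 h, depending on the section, and no rule covers more than one. This rests on the text alone.
- **Test:** two-sample wording does not match paired data. On the independent-groups reading at 1 h with ρ = 0.5, power is 78% against 92% at a true 10% difference, and 23% against 46% at 15%. These figures depend on the assumed correlation.
- **Decision wording:** TOST is probably meant, but the declaring sentences bypass it. Observed 1 h differences between about 12–17% (depending on ρ) and 20% meet those sentences and fail a paired TOST. The 50% against 5% contrast is conditional on the difference sentence deciding alone.

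Power at 2 h cannot be checked.

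**What to change.** 1. Reconcile the Protocol Summary with sections 4.2, 10.2 and 10.4 on which post-load time point or points decide. If more than one, require all to pass. Report fasting only as a check.
2. In section 10.4 and the Protocol Summary, replace the two-sample test with a paired (crossover) equivalence test.
3. Replace both declaring sentences, wherever they occur, with one rule: equivalence is concluded only if the paired 90% CI (TOST, 0.05 per side) lies wholly within the 20% margin. State in advance how the margin is expressed: either a limit in mmol/L fixed for each deciding time point, or a ratio of means within 0.80 to 1.20.

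**Cost.** Wording only; no extra women, visits or samples. The rule is stricter than the literal difference sentence. At 1 h and true difference 0, power with 28 pairs stays at about 99% or more: at least 99.3% with the fixed limit, and at least 98.8% with a paired Fieller interval for the ratio. The two forms are not interchangeable away from 0. At a true +10% and ρ = 0, the ratio form passes about 62% against 70% for the fixed limit. The ratio form needs no 2 h mean to define its limits; a fixed limit at 2 h would need a value that the protocol does not give.
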